### **1.3 Potential risks and benefits**

This study is designed as an observational study where enrolled patients are treated with ranibizumab according to the approved indication of neovascular AMD included in the local product SPC. Therefore, the benefit/risk associated with participation in this study is expected to be similar to the one described in the local product label.

## **2 Study Objectives**

The main objectives of this observational cohort study are to evaluate effectiveness of ranibizumab and also to evaluate safety and to describe follow-up as well as treatment patterns in treatment naive patients with neovascular AMD in routine clinical practice in Greece for the total study population.

### **2.1 Primary Objective**

- To evaluate the functional effectiveness of ranibizumab treatment in treatment naive patients with neovascular AMD in routine clinical practice in Greece as assessed by mean change in VA from baseline to month 12.

## 2.2 Secondary Objectives

- To evaluate the safety of ranibizumab as assessed by the type, frequency and severity of ocular and non-ocular AEs over 12 months of treatment with intravitreal injections of ranibizumab for the treatment of neovascular AMD in treatment naive patients in routine clinical practice in Greece.
- To describe treatment patterns of ranibizumab administration for neovascular AMD in routine clinical practice in Greece.
- To evaluate the anatomic effectiveness of ranibizumab treatment of neovascular in treatment naive patients with neovascular AMD in routine clinical practice in Greece as observed in this 1-year study duration and assessed by mean change in CRT from baseline to month 12.

## 2.3 Study outcome variables

### 2.3.1 Primary Outcome Variable

#### 2.3.1.1 Effectiveness variable

The primary efficacy variable will be evaluated with a functional parameter which is the mean change in VA from baseline visit to month 12 of treatment for the treated eye. Visual acuity will be measured according to the method used by each participating physician in their routine practice. In order to integrate different VA assessment methods for analysis, VA assessments performed using Snellen fraction or decimal score will be converted into an approximate ETDRS letter score equivalent.

### 2.3.2 Secondary Outcome Variables

#### 2.3.2.1 Safety variables

The safety objective of this study will be assessed based on the incidence, relationship and severity of ocular AE in the ranibizumab treated eye and of non-ocular AE during 12 months of follow-up.

#### 2.3.2.2 Treatment pattern variables

The number of ranibizumab injections administrated overall during treatment period, the number of visits and the average time interval (in weeks) between consecutive visits and injections will be summarized for the treated eye.

#### CONFIDENTIAL

This document is confidential and the property of individual. No part of it may be transmitted, reproduced, published, or used by other persons without prior written authorization from the author.

The reasons for the decision to treat or not (i.e. VA deterioration, OCT abnormality etc) will also be summarized in each visit. Reasons for treatment termination will be also evaluated.

Any topical use of antimicrobial agents pre- or post-injection will be evaluated.

### **2.3.2.3 Effectiveness variables**

Effectiveness of ranibizumab treatment will also be measured by mean change in CRT as an anatomic parameter. Mean change in CRT from baseline visit to month 12 of treatment for the treated eye will be evaluated as indicated by OCT measurements. For consistency and analyses' purposes, it is recommended that the same method of assessment and the same type of OCT machine be used throughout the study wherever possible.

## **3 Study Design**

This study is designed as an observational, prospective cohort, multicenter, open label, single-arm 1-year study in treatment naive patients with neovascular AMD who initiate treatment with intravitreal injections of ranibizumab in Greece. The study will be conducted in 10 ophthalmological clinics and practices throughout Greece.

During the study period it is planned to collect valid documentations on treatment of neovascular AMD from a representative sample of approximately 251 patients who meet the specific for study eligibility criteria. All the collected data will be entered in electronic Case Report Forms (CRFs).

[figure not shown]
The study will be conducted by medical retina specialists who are employed in 10 Ophthalmology Departments of public hospitals or private eye centers of Greece. The patients will be enrolled in the study upon signing an informed consent. Eligibility criteria will be assessed, baseline characteristics information will be collected and entered in the electronic CRFs and patients will be treated according to local routine clinical practice. There will not be applied a strict, mandated visit schedule or a mandated treatment regimen in order to collect available data in a real life setting in patients with neovascular AMD who initiate treatment with intravitreal injections of ranibizumab. The follow-up visits will take place at a frequency defined as per investigator's discretion in line with the routine clinical practice of

### **CONFIDENTIAL**

This document is confidential and the property of individual. No part of it may be transmitted, reproduced, published, or used by other persons without prior written authorization from the author.

participating investigators. It is advisable though that all visits during the study period to be documented in the CRF (Figure 1).

The overall planned duration of the study is anticipated to be 2 years. The enrollment period of subjects will continue until the required number of subjects will be enrolled or will last 12 months (whichever occurs earlier). Patients will be recruited from 10 Medical Retina Departments of outpatient Ophthalmology Clinics of public hospitals or private eye centers of Greece. Each enrolled patient will be followed for 12 months unless they discontinue or withdraw from the study. Every patient who successfully completes the study through Month 12 will be considered to have completed the study. A minimum of three visits per year is required in order to maintain a patient's participation in the study. The end of the study will be reached 12 months after last patient first visit and enrollment or when study participation for all patients is completed. No extension study is been planned.

\*There will not be applied a strict, mandated visit schedule during the observational period. The follow-up visits during observational period will take place at a frequency defined as per each investigator's discretion in line with their routine clinical practice. At least another one visit between Day 0 and Month 12 is required in order to maintain a patient's participation in the study.

**Figure 1: Schematic diagram of study design**

This study is designed as a non-interventional study. Strict compliance with the following rules will ensure the non-interventional nature of this study:

**CONFIDENTIAL**

This document is confidential and the property of individual. No part of it may be transmitted, reproduced, published, or used by other persons without prior written authorization from the author.

- All the enrolled patients should be treated with ranibizumab for neovascular AMD according to the approved local SPC of ranibizumab.
- The decision of the investigator to administer ranibizumab to the patient with neovascular AMD will be taken based on current clinical practice and before evaluation of the patient's eligibility for inclusion in the study.
- Participating subjects will not undergo any other diagnostic, therapeutic or observational procedures than those usually applied by their ophthalmologist in line with routine clinical practice.

The study is mainly based on collection of primary data by the study investigators at a frequency determined by the individualized scheme of follow-up and treatment in routine clinical practice. Information on medical history and previous treatment of the disease will be collected from the patients' medical records. Prospective data will be obtained during the visits of the study through the interview with the patient, the routine ophthalmologic and imaging examinations and according to each investigator's clinical practice (See Section 5).

## 4 Population: study enrollment and withdrawal

The study population will consist of patients diagnosed with neovascular AMD at one eye and who have not received any prior treatment for the particular condition. The decision of the investigator to treat neovascular AMD with intravitreal injections of ranibizumab has to be taken before the evaluation of the patient's eligibility for inclusion in the study.

During the study period it is planned to collect valid documentations on treatment of neovascular AMD from a representative sample of approximately 251 patients who meet the specific for study eligibility criteria and are treated at outpatient level in 10 Ophthalmology Departments of public hospitals or private eye centers of Greece.

Eligible patients must fulfill **all** the inclusion criteria and **none** of the exclusion criteria.

### 4.1 Inclusion Criteria

Patients eligible for inclusion in this study must fulfill all of the following criteria:

- Patients willing and able to provide written informed consent personally or by legal proxy. Written informed consent must be obtained before any study assessment is performed.
- Patients willing to comply with all study procedures and to be available for the duration of the study.
- Male or female  $\geq 50$  years old patients.
- Patients with an eye diagnosed with neovascular AMD which has not received any treatment for neovascular AMD and is decided to initiate treatment with ranibizumab.
- Patients where the decision of administration of ranibizumab for the treatment of neovascular AMD in accordance with the local ranibizumab SPC has been taken before the evaluation of the patient's eligibility for inclusion in the study.
- One eye of each patient will be included in the study. If both eyes are eligible at Baseline visit the eye to be selected as the study eye is the one the investigator deems to be more appropriate for study treatment and the study, based on CNV lesion characteristics in addition to visual impairment. If the fellow requires treatment because of visual impairment due to neovascular AMD, it may also be treated at the discretion of the investigator. This eye, however, will not be included in the study. Any treatment administered in the fellow eye will be recorded in electronic CRF, but only the data for the study eye will be included in the analysis of outcomes of the study.

## **4.2 Exclusion Criteria**

Patients fulfilling any of the following criteria are not eligible for inclusion in the study:

- Simultaneous participation in a study that includes administration of any investigational drug or procedure with interventions outside of routine clinical practice.
- Systemic treatment with any VEGF inhibitor within 6 months prior to study enrollment.
- Any prior therapy with any agent to treat neovascular AMD in the study eye.
- Patients who have any contraindications to the administration of ranibizumab according to the product SPC.
- Women of reproductive potential, defined as all women physiologically capable of becoming pregnant, unless they are using highly effective methods of contraception during study period treatment (e.g. total abstinence, sterilization, barrier methods of contraception, hormonal contraception, intrauterine system).
- Pregnant or nursing (lactating) women, where pregnancy is defined as the state of a female after conception and until the termination of gestation, confirmed by a positive hCG laboratory test.
- Men of reproductive potential unless using effective methods of contraception during study period (e.g. condoms).

## **4.3 Strategies for Recruitment and Retention**

Each patient documented in the study will be selected only based on eligibility according to inclusion and exclusion criteria. No further selection should be applied. Patients will be recruited from outpatient ophthalmology clinics of 10 public hospitals or private eye centers of Greece. Data collection will occur as patients are enrolled into the study. Patients will be enrolled consecutively in order to avoid any selection bias and thus to increase the likelihood of representativeness.

No compensation will be provided for study participation.

## **4.4 Premature patient withdrawal from the study**

Patients have the right to voluntarily withdraw from the study for any reason at any time. Patients may be considered withdrawn if they state an intention to withdraw, fail to perform at least three visits per year [including baseline and end of study (EOS) visits] or become lost to follow-up for any other reason.

### **CONFIDENTIAL**

This document is confidential and the property of individual. No part of it may be transmitted, reproduced, published, or used by other persons without prior written authorization from the author.

Investigator has the right to terminate a subject's participation if he/she judges that this is for the best interest of the subject.

#### **4.4.1 Reasons for Withdrawal**

Subjects are free to withdraw from participation in the study at any time upon request.

An investigator may terminate a study subject's participation in the study under the following circumstances:

- Withdrawal of study informed consent.
- If any medical condition, event or situation occurs such that continued participation in the study would not be in the best interest of the subject.
- The subject meets an exclusion criterion (either newly developed or not previously recognized) that precludes further study participation.
- Patient is not seen at the study center at least 3 times during the study period

#### **4.4.2 Handling of Subject Withdrawals**

If premature withdrawal occurs for any reason described above, the investigator must make every effort to determine the primary reason for a patient's premature withdrawal from the study and record this information on the Study Completion electronic CRF. However, patients are not obliged to justify their decision to withdraw.

For patients who are lost to follow-up (i.e. those patients whose status is unclear because they fail to appear for study visits without stating an intention to withdraw), the investigator should show "due diligence" by documenting in the source documents steps taken to contact the patient, e.g. dates of telephone calls, registered letters, etc.

Patient's withdrawal will not affect at any way their future medical care and treatment.

Patients who are prematurely withdrawn from the study will not be replaced by an equal number of newly enrolled patients.

## **4.5 Premature Termination or Suspension of Study**

This study may be suspended or prematurely terminated if there is sufficient reasonable cause. Written notification, documenting the reason for study suspension or termination, will be provided by the suspending or terminating party. Should this be necessary, the patient should be seen as soon as possible and undergo all assessments for EOS as described by the study protocol. The investigator may be informed of additional procedures to be followed in order to ensure that adequate consideration is given to the protection of the patient's interests. The principal investigator will be responsible to promptly inform institutional review boards (IRB) or independent ethics committees (IEC) of the early termination of the study and to provide the reason(s) for suspension or termination.

Circumstances that may warrant termination include, but are not limited to:

- Determination of unexpected significant or unacceptable risk to subjects.
- Insufficient adherence to protocol requirements.
- Data that is not sufficiently complete and/or evaluable.
- Determination of futility.
- The study can be terminated at any time for any reason by the Sponsor.

## **5 Visit schedule, assessments and data collection**

Table 5-1 lists all the data to be collected and entered in each patient's electronic CRF and indicates with an "X" the data when they are required to be collected (See also Figure 1).

There is no preset visit schedule, i.e. timing of actual patient visits is at the discretion of the treating physicians and sites will have the option of entering data from every patient visit during the study period. Physicians will be encouraged to follow-up with patients who have not been seen in the clinic for at least 3 months since the last visit to capture data as specified in Table 5-1.

If patients are not seen at least 3 times per year, they will be discontinued from the study.

All study visits should be documented in the electronic CRF. It is recommended that electronic CRFs are completed after every visit and at least within 1 month after the visit has occurred. However, whenever

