## **5.2 Observational period**

There is no preset visit schedule during the observational period. The visit frequency should be dictated by the local standard of care as this is determined by each investigator individually at each site. At least one visit between Baseline and EOS visit is required to be performed and reported in order to maintain a patient's participation in the study. However, it is recommended to report the data from every visit that will take place during the observational period.

Typical information to be collected during a visit during observational period includes:

- Date of follow-up visit (DD/MM/YYYY)
- Confirmation of patient's eligibility based on inclusion/exclusion criteria.
- Concomitant medications (systemic and ocular)
- Any visits performed between this and last documented visit that was not reported as part of the study
  - Number of visits
  - Date of visit (precise or approximate)
  - Administration of treatment or not
- Ophthalmic examination
- Visual acuity

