## **8.3 Primary Effectiveness Outcome Analyses Variables**

The analysis of the primary objective of the study will be performed in the per protocol set with available data pertaining to the study primary endpoint, i.e. baseline and 12-month VA data.

The mean change in VA from baseline to month 12 along with the 95% confidence interval (CI) will be calculated for subjects completing 12 months of follow-up. Paired sample t test will be applied to compare the 12-month VA to Baseline VA.

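### The three-visit minimum drops patients from the primary analysis who have both VA values, selecting on visit frequency, and its wording conflicts across sections

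*Protocol*

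**What the plan says.** The minimum visit count appears in several places in the protocol, with different force and different conditions.

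- **Section 5** is mandatory: "If patients are not seen at least 3 times per year, they will be discontinued from the study".
- **Section 4.4** is permissive. Patients *may* be considered withdrawn if they "fail to perform at least three visits per year [including baseline and end of study (EOS) visits". This is also where baseline and end of study (EOS) are said to count.
- **Section 4.4.1** lists, among the circumstances in which an investigator *may* end participation: "Patient is not seen at the study center at least 3 times during the study period".
- **Section 5.2** adds a reporting condition: "At least one visit between Baseline and EOS visit is required to be performed and reported".
- **Section 5** makes full entry of visits optional: "sites will have the option of entering data from every patient visit during the study period".
- **The synopsis, the schematic diagram and Section 3** repeat the requirement, as three visits per year or as one visit between Day 0 and Month 12. The synopsis and Section 3 also say that anyone who completes through Month 12 has completed the study.

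On the analysis side, Section 8.3 states: "The analysis of the primary objective of the study will be performed in the per protocol set with available data", and specifies the data needed as "i.e. baseline and 12-month VA data". Section 8.1 defines the per-protocol set as study completers without major deviations. It keeps non-completers' available data for every analysis except that of the primary objective.

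**The concern.** The primary endpoint needs two VA measurements, one at baseline and one at Month 12. The rule asks for a third contact in between, which the endpoint does not use. A patient without that contact can be removed from the primary analysis although nothing is missing.

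The number of visits and the interval between them are listed as treatment-pattern outcomes (Sections 2.3.2.2 and 8.4.2). Retention in the primary analysis therefore depends on something that happens after baseline and that the study sets out to describe. Section 4.3 enrols patients consecutively to limit selection bias, and Section 1.2 aims at a representative sample in everyday practice. A visit-count filter after enrolment works against both.

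Section 1.2 also says that outcomes in a cited German non-interventional study were probably affected by deficient monitoring. If the same holds here, removing the least-monitored patients makes the mean VA change look better than routine practice delivers.

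**Working it through.** **Step 1. Whom does the rule remove who would otherwise be analysed?** The inputs are the visit rule (Sections 4.4, 4.4.1, 5 and 5.2), the EOS window of 12 months ± 7 days (Section 5.3) and the data requirement (Section 8.3).

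| Visits | Both VA values possible? | Effect of the rule |
|---|---|---|
| Baseline only | No | Absent from the primary analysis anyway |
| Baseline and one interim visit, no EOS | No | Absent anyway |
| Baseline and EOS only | Yes | Removed because of the rule |
| Baseline, one interim visit seen but not reported, EOS | Yes | Meets Sections 4.4.1 and 5 (seen), fails Section 5.2 (reported): unclear |
| Baseline, at least one reported interim visit, EOS | Yes | Stays |

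Only the third row, and possibly the fourth, is an exclusion that the rule itself causes.

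**Step 2. The plan's own precision figure.** Section 8.5 gives SD 15.4 letters, a 95% CI and a margin of 2 letters.

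- n = (1.96 × 15.4 / 2)² = 227.8, rounded up to 228, as stated.
- 228 × 1.10 = 250.8, rounded up to 251, as stated.

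The sample size is not in dispute here. The 2-letter margin is the yardstick for the next step.

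**Step 3. Bias formula.** Among patients with both VA values, let s be the share removed by the rule. Let m_k be the mean change in those kept and m_r the mean change in those removed.

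- Mean in all of them: (1 − s)·m_k + s·m_r
- Mean reported: m_k
- Difference: s·(m_k − m_r) = s × deficit

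The documents give neither s nor the deficit. Both are assumptions below. Results are in letters.

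| Share removed | Deficit 3 | Deficit 5 | Deficit 10 |
|---|---|---|---|
| 2% | 0.06 | 0.10 | 0.20 |
| 5% | 0.15 | 0.25 | 0.50 |
| 10% | 0.30 | 0.50 | 1.00 |
| 20% | 0.60 | 1.00 | 2.00 |

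The upper-left part of the table is the more plausible. One intermediate visit in a year satisfies the rule, and most patients below three visits would have no Month-12 VA in any case.

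**Step 4. Precision.** The half-width is 1.96 × 15.4 / √n. With the planned 10% dropout, 251 × 0.90 = 225.9, so 225 whole patients remain and the half-width is 2.01. If the rule cost a further 5% of those enrolled, 251 × 0.85 = 213.35, so 213 remain and the half-width is 2.07. The effect on precision is small.

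**The case against.** The strongest defence is that the rule hardly bites. Baseline and EOS count, so a single visit in between is enough. Patients are to be treated according to the SPC, which Section 1.2 describes as monthly injections until maximum VA is reached. A patient with no contact between baseline and Month 12 would be unusual, and the under-monitored patients of ordinary practice, with three or four visits, stay in. This stands, and it is why the smaller bias figures are the more plausible.

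Several stronger readings are tempting, but the documents do not support them.

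- **A large, known bias.** A reader might take the share of all patients with fewer than three visits, say 5 to 15%, with a deficit of 8 to 10 letters, and get 0.05 × 8 = 0.4 to 0.15 × 10 = 1.5 letters. That share includes patients without Month-12 VA, who are missing with or without the rule. No section supports either range for the two-visit group.
- **Loss of safety and treatment-pattern data.** Section 8.1 keeps available data for all non-primary analyses. For a two-visit patient the rule is settled only at about Month 12, when little follow-up is left to lose.
- **Poor monitoring as the established cause of worse real-life results.** The passage in Section 1.2 concerns one cited study. It names two factors: monitoring, and insufficient use of diagnostic and retreatment criteria. It supports a likely direction, no more.
- **Patients failing on paperwork alone.** Table 5-1 and Sections 5.2 and 5.3 collect the number, dates and treatment of visits not otherwise reported. The gap comes from the reporting condition in Section 5.2 and is a matter of wording.
- **Exclusion steered by outcome.** Month-12 VA is known when a two-visit patient is classified, and the permissive wording leaves discretion. Nothing in the protocol shows that this is intended, and consistent wording would close the gap.
- **A material loss of precision.** Section 4.4 treats failing the visit minimum as a form of withdrawal, so these patients may already fall within the planned 10% dropout.

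It can also be argued that a patient seen at Month 12 is a completer under Section 3. But the same paragraph makes three visits a condition of staying in the study, so the patient's status is at best contradictory.

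**Conclusion.** The point holds for a narrow group: patients seen at baseline and within the Month-12 window but not in between. Under the mandatory wording of Section 5 they are discontinued and leave the per-protocol primary analysis with both VA values on record. Under Sections 4.4 and 4.4.1 their fate is discretionary. If an interim visit took place but was not reported, the sections disagree on whether the rule was met.

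The harm falls mainly on the primary VA result. A too-favourable mean change is the likely direction, inferred from the protocol's own remark on monitoring. The size cannot be derived from the documents: 0.06 letters at 2% and 3 letters and 1.0 letter at 10% and 10 letters are illustrations on assumed inputs, to be read against the 2-letter margin, with the lower end more plausible. The reason to act is that the selection is avoidable, runs against the study's stated purpose and costs very little to remove.

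**What to change.** 1. State that visit count alone is not a ground for discontinuation from the study or for exclusion from the primary analysis.
2. Include every eligible patient with baseline and Month-12 VA in the primary analysis, whatever the number of visits. The paired t test of Section 8.3 needs only those two values, so the method does not change.
3. Report the proportion of patients with fewer than three visits as a treatment-pattern result under Section 8.4.2.
4. Reconcile the synopsis (the rows on duration and on clinical assessments), the schematic diagram and Sections 3, 4.4, 4.4.1, 5 and 5.2, so that *may* against *will* and *seen* against *reported* no longer conflict.

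The cost is one protocol amendment and the acceptance of some patients with sparse interim data. No visit or procedure is added.
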